## 8.2 Aim II

The second study aim is to establish performance characteristics of each of the following structural analytes, which will be measured for each target lesion by both vascuCAP™ and two radiologists' performing manual contouring:

- a. Remodeling ratio
- b. Percent Stenosis
- c. Maximum wall thickness

This study aim also applies similar analysis to the hemodynamic analyte endothelial shear stress since even though the computational method differs, yet it still depends on the location of contours

The vascuCAP™ measurements will be made under two scenarios: vascuCAP™ fully automated (fully automated mode) and vascuCAP™ followed by adjustments by a radiologist (semi-automated mode).

In the neck and leg, for each structural analyte, we will first visually compare vascuCAP™'s measurements to the median of the two radiologists' measurements. We will plot the radiologists' median value vs. the value measured by vascuCAP™ in each vascuCAP™ mode. Any analyte not measurable will also be indicated on the plot using a different plotting character. The resulting plot will be inspected visually for the following:

1. Limits of vascuCAP™'s quantitation;
2. Associations between the magnitude of the analyte and the magnitude of the discrepancy between vascuCAP™ and the radiologists' measurements; and
3. Associations between the magnitude of the analyte and heteroscedasticity in the vascuCAP™ measurements.

If the plots of neck and leg have similar distributions, then the data from these sites will be pooled; otherwise, separate analyses will be performed. Since the radiologists' manual contouring has both bias and measurement error, rather than assessing agreement, we will estimate the *interchangeability* of vascuCAP™'s structural measurements with the manual contouring by radiologists. The individual equivalence criterion [16, 17] will be estimated as follows:

$$\widehat{IEC} = \sqrt{\sum_{i=1}^n (X_i - Y_{i1})^2} - \sqrt{\sum_{i=1}^n (Y_{i1} - Y_{i2})^2}$$

where  $X_i$  is the measurement for the i-th case by vascuCAP™,  $Y_{i1}$  is the measurement for the i-th case by the first radiologist using manual contouring, and  $Y_{i2}$  is the measurement for the i-th case by the second radiologist using manual contouring. IEC is a measure of the expected difference between vascuCAP™'s measurements and a radiologist's measurements with manual contouring, after adjusting for the expected difference between two radiologists' measurements with manual contouring. IEC will be estimated for both vascuCAP™ fully-

automated and vascuCAP™ semi-automated. 95% bootstrap CIs will be constructed for the IEC.

For each of the structural analytes, we will estimate the reproducibility of the measures for different factors: different institutions, different scanner models, different field strengths, and with respect to ranges documented in the literature according to collected patient characteristics. We will estimate the IEC for these different factors, and we will construct CIs for the difference between the IECs using bootstrap simulations.

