A linear model will be fit (for all of the data or for a subset of histopathology values, depending on the findings from the plot) where the dependent variable is the vascuCAP™ measurement ( $X$ ) and the independent variable is the histopathology value ( $Y$ ). Generalized estimating equations (GEEs) (to account for the fact that some patients will have more than one target lesion) will be used to estimate the linear function:  $E(Y|X) = \beta_0 + \beta_1 X$ . An unstructured working covariance will be used. We will construct a 95% CI for the intercept  $\beta_0$  using a t-statistic as the pivotal statistic. CIs not containing 0 indicate fixed bias. We will also construct a 95% CI for the slope  $\beta_1$ . CIs not containing 1 indicate proportional bias [11].

The precision of the vascuCAP™ measurements will be estimated by the standard deviation:

$$\sqrt{\frac{1}{n-1} \sum_{i=1}^n (Y_i - X_i - \bar{d})^2} \text{ where } \bar{d} \text{ is the sample mean of the differences, } \bar{d} = \frac{1}{n} \sum_{i=1}^n (Y_i - X_i) \text{ [1].}$$

We will construct a 95% CI for the precision using bootstrap methods.

We will plot the bias profile (plot of bias of measurements for various ranges of histopathology values vs. the histopathology value) and precision profile (plot of standard deviation of vascuCAP™ measurements from patients with similar histopathology values vs. the histopathology value) as visual summaries of vascuCAP™ performance for the bias and precision components, respectively [12].

In addition to reporting these technical performance characteristics of the volume measurements, we will also report i) the coverage probability (CP) and ii) a discrimination index [11]. The CP is the probability that the absolute difference between the value measured by vascuCAP™ and the value measured by histology is less than  $d_0$ , i.e.  $\pi = \Pr(|Y - X| < d_0)$ . We will plot the CP for a range of values for  $d_0$ . The discrimination ability of the measurements, i.e. the ability of vascuCAP™ to discriminate between different magnitudes of histopathology values, will be measured using the area under the ROC curve for continuous measures [13]. 95% CIs for the CP and ROC area will be constructed using methods for clustered binary data [14] and clustered ROC data [15], respectively.

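### The Aim II interchangeability formula omits 1/n and compares vascuCAP with one unspecified radiologist, so its size depends on the case count and its value can depend on the reader label

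*Combined protocol and SAP*

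**What the plan says.** Section 8.2 covers remodeling ratio, percent stenosis and maximum wall thickness, and applies a similar analysis to endothelial shear stress. Each structural analyte is one "which will be measured for each target lesion by both vascuCAP™ and two radiologists' performing manual contouring". The estimator is "IEC} = \sqrt{\sum_{i=1}^n (X_i - Y_{i1})^2} - \sqrt{\sum_{i=1}^n (Y_{i1} - Y_{i2})^2", with X for vascuCAP. The first manual value, Y1, "is the measurement for the i-th case by the first radiologist using manual contouring"; Y2 is the second radiologist's value.

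The text after the formula gives the intended meaning: "IEC is a measure of the expected difference between vascuCAP™'s measurements and a radiologist's measurements with manual contouring", adjusted for the difference expected between two radiologists. On subgroups it says: "We will estimate the IEC for these different factors, and we will construct CIs for the difference between the IECs using bootstrap simulations". The factors are institution, scanner model, field strength and patient characteristics.

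The plots that precede the estimate treat the readers alike: "we will first visually compare vascuCAP™'s measurements to the median of the two radiologists' measurements".

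Sections 4 and 8 say that one of the two radiologists also does the vascuCAP-aided contouring, after a wash-out and blinded to their own manual results. Neither section, nor 8.2, says whether this is the first or the second radiologist.

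**The concern.** The formula and its description conflict. An expected difference is a per-case quantity, whereas a root of a plain sum grows with the number of cases. An analyst who codes section 8.2 literally would report a number that cannot be read in millimetres or percentage points.

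The reference is also one-sided. The section justifies interchangeability over agreement with the words "Since the radiologists' manual contouring has both bias and measurement error", yet it measures the device against one reader only and does not say how that reader is chosen.

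Objective II is primary, and the IEC is the only numerical measure of agreement with the radiologists in section 8.2; the comparison with their median is visual. No IEC margin is set, so a reader must judge its size and its contrasts between factors, which are what the missing 1/n affects. Section 4 says that phase-two data give the definitive results for the 510(k) application.

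**Working it through.** The plan gives no expected IEC, margin or Aim II sample size, so there is no figure of its own to reproduce. The check is algebra on the printed formula, followed by illustrations whose inputs are assumed.

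**1. Scaling with n.** Since sqrt(sum) = sqrt(n) x sqrt(mean),

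IEC as printed = sqrt(n) x [RMS(X-Y1) - RMS(Y1-Y2)].

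Multiplying by sqrt(n) cannot change the sign, in the data or in any bootstrap resample. So the sign of a single IEC, and whether its percentile interval covers 0, stay the same. The size does not:

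- Patients: section 4 allows 35 to 75 in phase two. sqrt(75/35) = 1.46.
- Lesions: section 8.1 assumes one lesion per carotid patient and two per PAD patient. The phase-two minimum gives 25 + 2 x 10 = 45. Seventy-five patients at the phase-one split (an assumption for phase two) give 55 + 2 x 20 = 95. sqrt(95/45) = 1.45.

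**2. Contrasts between factors.** If two groups of sizes n1 and n2 have the same true performance, the printed IECs differ by about [sqrt(n1) - sqrt(n2)] x [RMS(X-Y1) - RMS(Y1-Y2)]. This is zero only if the groups are equal in size or the two RMS values are equal. To show the effect on the intervals, take Y1 and Y2 as N(0, 1) and X as N(0, k^2), with identical performance in both groups. Lesions are treated as independent; there are 4,000 data sets, 400 resamples and percentile 95% intervals (simulation SE 0.4 to 0.8 points). Share of intervals excluding 0:

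| Group sizes | k (device SD / reader SD) | As printed | With 1/n |
|---|---|---|---|
| 60 v 15 | 2 | 30.1% | 8.8% |
| 60 v 15 | 1.5 | 15.6% | 8.6% |
| 60 v 15 | 1 (equal RMS) | 7.0% | 7.8% |
| 25 v 10 | 2 | 14.4% | 9.5% |
| 25 v 10 | 1.5 | 11.1% | 10.3% |
| 38 v 37 | 2 | 6.6% | 6.6% |

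Lesion-sized groups show the same pattern at k = 2: 35.8% v 8.7% for 76 v 19, and 13.0% v 8.6% for 30 v 15. Adding 1/n removes the case-count effect; it does not bring a small-sample percentile bootstrap to 5%.

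**3. The label 'first'.** The second root is unchanged if the readers are swapped. The first is not, so the expected IEC depends on the label whenever the mean of (X-Y1)^2 differs from the mean of (X-Y2)^2. Per-case values with device SD 1 and no device bias (all inputs assumed):

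- Unbiased readers, SDs 0.8 and 1.2. More precise reader first: sqrt(1 + 0.64) - sqrt(0.64 + 1.44) = -0.16. Less precise reader first: sqrt(1 + 1.44) - sqrt(2.08) = +0.12. Using both readers: sqrt(2.04) - sqrt(2.08) = -0.01.
- Both reader SDs 1, one reader biased by 1. Unbiased reader first: sqrt(2) - sqrt(3) = -0.32. Biased reader first: sqrt(3) - sqrt(3) = 0.00.
- Both reader SDs 1, biases +0.5 and -0.5. Either label: sqrt(2.25) - sqrt(3) = -0.23. The readers differ in bias, yet the label has no effect.

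With unbiased readers and reader A first, the sign is that of (device SD minus reader B's SD). The label therefore reverses the sign only when the device SD lies between the two reader SDs. With reader SDs 0.8 and 1.2 and device SD 2, the values are +0.71 and +0.89.

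**4. The editor in semi-automated mode.** If radiologist 1 edits, X and Y1 share that reader's contouring habits, so the first root is a same-reader difference and the second a between-reader one. Let style variance be t^2, residual variance s^2, and c the share of the editor's style carried into X. The shift, relative to the between-reader RMS, is

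[sqrt((1-c)^2 t^2 + 2s^2) - sqrt((1+c^2) t^2 + 2s^2)] / sqrt(2t^2 + 2s^2).

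For t^2/s^2 from 0.25 to 4 and c of 0.5 or 1, it runs from -5% to -55%. So wide a range from assumed inputs is not an estimate. If radiologist 2 edits, this shift does not arise.

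**The case against.** The strongest reply is that the missing 1/n is a notation slip: the adjoining prose tells the analyst what to compute. That is probably right, but the formula is what will be coded, and loss in PDF conversion is an unlikely cause because the Aim I precision formula kept its divisor: "1}{n-1} \sum_{i=1}^n (Y_i - X_i - \bar{d})^2".

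The reply is also right that several stronger readings go too far:

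- A reader might infer that every IEC conclusion is invalid. It is not: the sign of a single IEC and its coverage of 0 survive.
- A reader might infer that subgroup contrasts will be badly inflated. The plan gives no counts by institution, scanner model or field strength. The 30% figure needs an assumed 4:1 split and device error twice a reader's; at moderate splits and 1.5 times the effect is small. Section 8.2 plans intervals for these differences, not tests. The simulation ignores the within-patient correlation of 0.5 that section 8.1 assumes.
- A reader might infer that any difference between the readers makes the label matter, or that it generally flips the sign. Neither follows, as step 3 shows.
- A reader might infer that the semi-automated result is biased. The documents do not say that radiologist 1 edits, and they require wash-out and blinding. Those measures limit memory, though not a reader's habitual style, so the risk is conditional.

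**Conclusion.** The formula is wrong as written. Two facts are exact: the printed IEC is sqrt(n) times the per-case quantity, and its first term uses only one radiologist, chosen by no stated rule. The size therefore grows 1.46-fold from 35 to 75 cases (1.45-fold from 45 to 95 lesions), and the planned contrasts mix performance with group size when groups are unequal and the two RMS values differ. The expected IEC depends on the reader label when the device's mean squared difference from one reader differs from that from the other, and for some inputs the label changes the sign.

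The simulated percentages and label values are illustrations under assumed error sizes and splits. The editor question is a secondary safeguard: it matters only if radiologist 1 edits, and then favours interchangeability by an amount that the documents do not allow to be estimated. This should be fixed before the phase-two analysis; it does not undermine the design.

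**What to change.** - **Both modes:** put 1/n inside both roots.
- **Fully automated mode:** IEC = sqrt(mean of [(X-Y1)^2 + (X-Y2)^2]/2) - sqrt(mean of (Y1-Y2)^2). This gives the same value whichever reader is called first.
- **Semi-automated mode:** name the editing radiologist before phase two and compare X only with the other radiologist's manual contour, Y_other: IEC = sqrt(mean of (X-Y_other)^2) - sqrt(mean of (Y1-Y2)^2).
- **Comparing modes:** use Y_other as the reference for both, since the two formulas above otherwise use different references.

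Both radiologists already contour every case, so this is SAP wording only, with no new data. There are two downsides. The semi-automated IEC may look less favourable, and it still rests on one reference reader, so some dependence on the choice of editor remains.

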## 8 STATISTICAL ANALYSIS

A two-phase study is proposed. In the first phase, 75 surgical patients will be recruited as part of a training set; aims I-III will be evaluated with this set. In the second phase, at least 35 surgical patients will be recruited (possibly more, depending on the results of the first phase). Data from the second phase data will be used in the 510(k) application (i.e. Report of the results of the performance of the functional and structural analytes) and as additional training data for Aim III.

Two radiologists will be recruited for the study. The two radiologists will independently perform the manual contouring for all study patients, and one of these two radiologists will also perform the vascuCAP™ aided contouring after a sufficient wash-out period after the manual contouring and with appropriate blinding to their manual results.

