The volume measurements are considered the most critical because they will be used to construct a score to predict rupture risk. Thus, we considered the width of 95% confidence intervals for the bias and the between-subject variance as a function of sample size (see Tables 1 and 2). The following assumptions were made: 1) the volume measurements are normally distributed; 2) carotid artery patients contribute one target lesion each, while PAD patients contribute two target lesions each; 3) target lesions from the same patient are moderately correlated ( $r=0.5$ ); 4) one-quarter of all patients will be PAD patients; 5) results from femoral and carotid target lesions can be pooled; 6) the average volume of an analyte is  $25\text{mm}^3$ ; and 6) the precision of the vascuCAP™ measurements is 10-20% of the volume of analyte.

From Table 4, if the SD was 15% of the mean volume, then we expect to be able to construct a 95% CI for the bias of total width of 10% with  $n=35$ . If the SD was 20%, then with  $n=35$  we expect to construct a 95% CI of total width of 14%. Similarly, from Table 5, if the SD was 15% of the mean volume, then with  $n=35$  we expect to be able to construct a 95% CI for the precision of total length 8%; if the SD was 20%, then we expect to be able to construct a 95% CI for the precision of total length 11%. We plan to recruit 75 patients (55 carotid artery patients and 20 PAD patients) in phase one to account for the fact that the estimates of bias and

precision may need to be reported in strata based on the magnitude of the histopathology volume and/or by anatomic location. In phase two we plan to recruit at least the minimum of 35 (25 carotid artery patients and 10 PAD patients) and possibly more depending on the results of the training set.

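### The bootstrap interval for the IEC in Aim II is in practice conditional on the two study radiologists, while the text reads it as interchangeability with radiologists in general.

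*Combined protocol and SAP*

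**What the plan says.** Section 8 sets the reader panel: "Two radiologists will be recruited for the study". Both contour all patients by hand.

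Section 8.2 explains why it uses an interchangeability criterion: "Since the radiologists' manual contouring has both bias and measurement error, rather than assessing agreement". The target is the interchangeability of vascuCAP's "structural measurements with the manual contouring by radiologists". The individual equivalence criterion (IEC) is the root of the summed squared differences between vascuCAP (X) and reader 1 (Y1), minus the same quantity for reader 1 and reader 2 (Y2). Y1 "is the measurement for the i-th case by the first radiologist using manual contouring", and it appears in both terms. The section interprets the result in general terms: "IEC is a measure of the expected difference between vascuCAP™'s measurements and a radiologist's measurements with manual contouring".

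On uncertainty it says only this: "95% bootstrap CIs will be constructed for the IEC". It names no resampling unit, reader variance component, margin or decision rule, and it does not limit the conclusion to the two readers.

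**The concern.** The claim and the interval refer to different things. The claim is about radiologists as a class. The interval is built from two of them, and a reader's systematic offset is the same in every case that reader contours. Resampling cases reproduces the case-to-case noise but never varies the offsets.

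The IEC can then be clearly positive or clearly negative only because the two recruited readers happen to share an offset or to differ in one. More patients do not help, because the interval tightens around a value specific to these two people. The favourable direction matters as well: two readers who differ systematically enlarge the second term and make the device look interchangeable.

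Aim II is a primary objective (Section 3.1), and Section 4 makes phase two the source of the definitive results for the 510(k).

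**Working it through.** **Inputs from the documents.** There are two readers (Section 8). The phase two minimum is given in Section 8.1: "In phase two we plan to recruit at least the minimum of 35 (25 carotid artery patients and 10 PAD patients"). Phase one has 75 patients (55 carotid, 20 PAD), and 75 is also the most that Section 4 foresees for phase two. Section 8.1 assumes one lesion per carotid patient, two per PAD patient, and a within-patient correlation of 0.5. That gives 25 + 2×10 = 45 lesions, or 55 + 2×20 = 95. The plan gives no sample size or precision figure for the IEC, so there is nothing to reproduce first.

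**Input assumed.** The between-reader bias SD (sb), relative to one reader's per-lesion error SD (se), is not in the documents. It is shown over a range.

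**Step 1: what can be resampled.** Redrawing two readers with replacement would often pair one reader with himself or herself and make the second term zero. That leaves cases or patients. This is inferred from the design; the plan does not say it.

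**Step 2: what the IEC estimates.** Let X come from a third radiologist with bias b3, let readers 1 and 2 have biases b1 and b2, and let all three have independent errors with SD se. Per lesion, the IEC tends to

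√[(b3 − b1)² + 2se²] − √[(b1 − b2)² + 2se²]

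(The printed formula does not divide by n; this changes the scale, not the sign.) The expression is zero only if |b3 − b1| = |b1 − b2|. Over random draws of readers it is symmetric about zero, but for any given trio it generally is not zero. Example with se = 1 and sb = 1: the SD of a difference between two reader biases is √2 = 1.41. If reader 3 shares reader 1's bias and readers 1 and 2 differ by 1.41, the limit is √(0 + 2) − √(2 + 2) = 1.41 − 2.00 = −0.59. With the two gaps exchanged it is +0.59. All three readers come from the same population in both cases.

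**Step 3: simulation.** Three exchangeable readers were drawn with normal biases (SD sb) and equal error SDs, the third taking vascuCAP's place. The interval was a 95% percentile bootstrap over patients (600 resamples, 1,500–2,000 trials per setting). Share of intervals excluding 0, as a range where repeat runs differed:

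| sb/se | 35 patients | 75 patients |
|---|---|---|
| 0 | 7–8% | 6% |
| 0.25 | 7–10% | 9–10% |
| 0.5 | 18–22% | 27–30% |
| 0.75 | 34–37% | 45–46% |
| 1 | 46–50% | 56–60% |

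At ratio 2 the shares are about 73% and 80%. The exclusions split about evenly by direction: with 35 patients and ratio 1, about 24% look worse than a radiologist and 24% look closer. Averaging the device difference over both readers leaves the rate unchanged (51% at ratio 1 with 45 independent cases, against 50% for the printed form).

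**Step 4: what the interval does cover.** Coverage of the IEC conditional on the realised reader biases is about 92–95% at 35 or more cases. The interval works for these two readers. It omits the variation between readers.

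**Step 5: whether separating bias from precision would rescue a general claim.** It would not. In the same third-radiologist setting with 35 patients, the interval for the mean difference X − Y1 excludes 0 in about 30% of trials at ratio 0.25 and about 75% at ratio 1. An IEC built from the SDs of the differences stays at about 6–8% only if all readers have the same error SD. If error SDs vary modestly (SD 0.25 on the log scale, assumed), its interval excludes 0 in about 25% of trials with 35 patients and 35–39% with 75.

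**The case against.** The strongest reply is that no test is being failed. Section 8.2 only estimates the IEC and gives an interval. It sets no null value, margin or two-sided rule, and a negative IEC means that vascuCAP is closer to reader 1 than reader 2 is, which nobody would call a failure of interchangeability. Counting only the unfavourable direction halves the rates: about 10% at ratio 0.5 and 24% at ratio 1 with 35 patients, against 3–4% with no reader bias. All of this stands. A reader might infer that the planned analysis would wrongly reject a genuine radiologist about half the time; the documents do not support that, because they contain no rejection rule.

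The size also depends on a ratio that the documents do not give. At 0.25 or below the effect with 35 patients is close to the no-bias baseline. About half applies to ratio 1 with 35 patients, and it is not an upper bound either, since larger samples or larger reader bias give more. This stands too.

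That the bootstrap resamples only cases is an inference, though no workable alternative is apparent with two readers.

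None of this removes the mismatch. The section concedes reader bias, generalises to radiologists, and offers an interval that cannot reflect how radiologists differ.

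**Conclusion.** The point holds as a limit on what the interval supports. The 95% bootstrap interval is valid, to about 92–95%, for the two study radiologists. It does not cover a statement about radiologists in general.

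For a third exchangeable radiologist with 35 patients, it would exclude 0 in about 7–8% of trials with no reader bias, and in about 9%, 20% and 48% at bias-to-error ratios of 0.25, 0.5 and 1. From 0.5 upwards the rate grows with sample size, to 56–60% at 75 patients and ratio 1. These figures assume normal biases and errors, equal error SDs, patient-level resampling and the stated ratios. They describe lack of coverage for the general claim, split evenly by direction, and not the type I error of a stated test.

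It is also tempting to infer that removing the mean differences and using an SD-based IEC would support a general claim without more readers. Step 5 shows that it would not: two readers represent a population of readers no better in their variances than in their biases.

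**What to change.** 1. State in Section 8.2 that the IEC and its interval are conditional on the two study radiologists, and name the resampling unit.
2. Word the Aim II conclusion, and the corresponding statement in the 510(k), as interchangeability with these two readers.
3. Alongside the IEC, report descriptively the mean differences (vascuCAP minus reader 1, vascuCAP minus reader 2, reader 1 minus reader 2) and the SDs of the differences. This shows whether the IEC is driven by a systematic offset between the readers.
4. Do not base general statements about radiologists on those mean differences or on an SD-based IEC, since both are specific to these readers.

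The cost is a few sentences in the analysis section and a few lines of code, with no new patients or readers. The price is a narrower claim. A claim about radiologists in general would need more readers and a reader-level variance component.
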